Consecutive patients aged 45 years or older undergoing colonoscopy for screening, surveillance, and positive FIT will be considered for enrollment [28]. Exclusion criteria will include familial adenomatous polyposis and hereditary non-polyposis CRC syndrome, personal history of CRC or inflammatory bowel disease, previous colonic resection, obstructive lesions of the colon, gastrointestinal bleeding, allergy to fentanyl or midazolam, American Society of Anesthesiology (ASA) classification of physical status grade 3 or higher (e.g. controlled congestive heart failure, stable angina, previous heart attack, poorly controlled hypertension, morbid obesity, chronic renal failure, bronchospastic diseases with intermittent symptoms), mental retardation, pregnancy, and refusal to provide a written informed consent.

Randomization

Patients will be randomized in a 1:1 ratio to undergo either the CO2 insufflation colonoscopy (CO2 group) or WE colonoscopy (WE group). Randomization will be carried out by a computer-generated random sequence. Stratification based on

colonoscopists and colonoscopy indications (screening, surveillance, and positive FIT) will be performed. Individual random sequence will be placed in an opaque envelope kept by an independent research assistant not directly involved in this study, which will be opened immediately before the procedure.

Bowel Preparation and Sedation

Patients will be instructed to eat low-residual foods for two days before colonoscopy. Oral and written instructions on the split-dose bowel preparation (Polyethylene glycol solution) will be provided to all patients. Colonoscopy will be performed without sedation or with moderate sedation (intravenous fentanyl plus midazolam). Moderate sedative agents will be administered by endoscopists.

Colonoscopy Procedures

Colonoscopies will be performed by two board-certified colonoscopists ([name], [name]). Standard colonoscopes (CF-Q260AL/I; Olympus Medical Systems Corp., Tokyo, Japan) will be used. All colonoscopists have performed more than 1000 conventional colonoscopies. Hands-on coaching by a WE expert ([name]) to standardize the WE method has been completed. Each colonoscopist has or will have completed 100 cases of WE learning curve. [name] will be involved in the study design, data analyses, and report preparation, but not in patient enrollment. All the colonoscopic procedures will be recorded.

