All colonic polyps removed during procedures will be sent for histological examination with clear labeling of location and sequences of colonoscopy. The location of colonic polyps will be defined according to the anatomical distribution. Right colon will be defined as cecum, ascending colon, and hepatic flexure. Proximal colon will be defined as right and transverse colon. Diminutive polyps will be defined as polyps with size ≤ 5 mm. Small polyps will be defined as polyps with size 6-9 mm. Large polyps will be defined as polyps with size ≥ 10 mm. Adenomas will include all adenomas and sessile serrated adenoma. Advanced adenomas will be defined as those lesions with one of the following criteria: 1) lesions larger than 10 mm in diameter; 2) lesions with a villous component; 3) lesions with high-grade dysplasia; and 4) lesions with invasive features.

ADR will be defined as the proportion of colonoscopies with at least one adenoma.

Advanced ADR will be defined as the proportion of colonoscopies with at least one advanced adenoma. Mean adenoma per procedure (MAP) will be defined as the total number of adenomas detected divided by the number of colonoscopies. Mean adenoma per positive procedure (MAP+) will be defined as the total number of adenoma detected divided by the number of colonoscopies in which at least one adenoma is found. Mean additional adenomas detected beyond the first adenoma per positive procedure (ADR-Plus) will be defined as the mean number of adenomas detected after the first adenoma in procedures in which at least one adenoma is found.

Lesions detected on the tandem right colon examination will be used for the calculation of adenoma or polyp miss rate. Right colon AMR and hyperplastic polyp miss rate (HPMR) will be calculated as the number of adenomas and hyperplastic polyps missed in the first right colon examination divided by the total number of adenoma and hyperplastic polyps detected during both the first and tandem right colon examinations.

Study Outcomes

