The primary outcome is the right colon combined AMR and HPMR. Secondary outcomes include right colon AMR, right colon HPMR, overall ADR, right colon ADR and HPDR after the first examination, combined right colon ADR and HPDR after the first and tandem examinations, overall advanced ADR, right colon advanced ADR, overall MAP, right colon MAP, overall MAP+, right colon MAP+, overall ADR-Plus, and right colon ADR-Plus. Procedure related parameters, including bowel cleansing, insertion and withdrawal times, duration of tandem right colon examination, volume of water infused and aspirated during insertion and withdrawal, and number of abdominal compressions and/or position change, are also evaluated.

Sample size estimation

The sample size estimation is based on the assumption that WE colonoscopy reduces right colon combined AMR and HPMR compared to conventional CO2 insufflation colonoscopy. We estimate the overall right colon combined AMR and HPMR in the CO2 group to be 30% [30,31]. According to our previous study, the average detected number of right colon adenoma and hyperplastic polyp is 0.8 per subject after first right colon examination [32]. To show a clinically important improvement of AMR reduction by the WE colonoscopy, we assume that WE colonoscopy should reduce the AMR by 15%. With a statistical power of 80% and a two-side significance level of 0.05, 131 patients will be needed in each study arm. To account for dropouts, incomplete procedures, and inadequate preparation, an additional 10% will be enrolled. Therefore, a total of 292 patients (146 patients in each group) will be enrolled.

Statistical analysis

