Summary statistics will be presented as frequencies and percentages in the case of categorical variables and as the means with standard deviations (SD) in the case of continuous variables. Analysis will be performed by using an Intention-to-treat (ITT) approach. Interim analysis will be performed after enrollment of 131 patients. Student's *t*-test for continuous factors, Wilcoxon rank sum test for ordinal variables (such as polyp size), and Chi-square test for categorical variables will be used to assess differences in demographic and clinical characteristics of patients in each group. Factors associated with adenoma detection by the first examiner will be identified by univariate analysis. Factors with a *P* value <0.1 on univariate analysis will be further entered into forward stepwise logistic regression analysis. The adjusted odds ratio with 95% confidence interval (CI) will be used to describe the

influence of various factors on adenoma detection. All statistical analyses will be performed by using SAS version 9.3 or later (SAS Institute Inc., Cary, NC, USA). The criterion for statistical significance will be P value <0.05 .

REFERENCES:

6. le Clercq CM, Bouwens MW, Ronagh EJ, et al. Postcolonoscopy colorectal cancers are preventable: a population-based study. *Gut* 2014;63:957-963.
7. van Rijn JC, Reitsma JB, Stoker J, Bossuyt PM, van Deventer SJ, Dekker E. Polyp miss rate determined by tandem colonoscopy: a systemic review. *Am J Gastroenterol* 2006;101:343-350.

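### No test is named for the lesion-level primary outcome, and neither the analysis nor the sample size allows for several lesions coming from one patient

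*Combined protocol and SAP*

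**What the plan says.** - **Randomization:** the unit is the patient: "Patients will be randomized in a 1:1 ratio".
- **Study Outcomes:** "The primary outcome is the right colon combined AMR and HPMR".
- **Definition:** the miss rate is the number of adenomas and hyperplastic polyps missed at the first right colon examination, "divided by the total number of adenoma and hyperplastic polyps detected during both the first and tandem right colon examinations". Numerator and denominator are both counts of lesions.
- **Statistical analysis:** after the t-test and the Wilcoxon test (polyp size is the example given for the latter), "Chi-square test for categorical variables will be used to assess differences in demographic and clinical characteristics of patients in each group". The only model is a stepwise logistic regression for adenoma detection by the first examiner, and the only confidence interval is for its odds ratio. The section adds an ITT approach, a P<0.05 criterion and SAS.
- **Sample size estimation:** a miss rate of 30% with CO2, a reduction of 15%, and a figure from the investigators' own published trial: "the average detected number of right colon adenoma and hyperplastic polyp is 0.8 per subject after first right colon examination". It concludes: "With a statistical power of 80% and a two-side significance level of 0.05, 131 patients will be needed in each study arm". A 10% allowance brings this to 146 per arm, 292 in total.

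No section mentions correlation between lesions of the same patient, a design effect or a clustered method.

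**The concern.** The test of the main hypothesis is left open until data are available. A reader who looks for a default finds one simple test for a proportion, the chi-square, and would apply it to a two-by-two table of lesions. That test treats every lesion as an independent observation. Lesions in one right colon share the same bowel preparation, anatomy, insertion and first examiner, so whether one is missed is plausibly related to whether the next is missed. The Introduction itself links the expected benefit of water exchange to cleaning and calls the right colon usually the worst prepared segment.

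If the correlation is positive, the lesion-level P value is too small and an interval built the same way is too narrow. The power of the planned enrolment is also unknown, because it depends on how many lesions patients have and how strongly their outcomes are correlated.

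**Working it through.** **1. Reproducing 131 per arm.** Inputs from Sample size estimation: 30% v 15% (the reduction read as absolute, since a relative 15%, 30% to 25.5%, would need about 1,554 per arm), two-sided 0.05, power 80%.

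- Unpooled formula: (1.960 + 0.842)² × (0.30×0.70 + 0.15×0.85) / 0.15² = 117.7.
- With continuity correction: 117.7/4 × (1 + √(1 + 4/(117.7×0.15)))² = 130.7, so 131.
- Fisher exact power: 0.797 at 130 per arm, 0.801 at 131.
- 131/0.9 = 145.6, so 146 per arm and 292 in total.

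Both routes give 131 from one independent observation per patient. The 0.8 lesions per subject is not needed to reach it.

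**2. Lesions per patient.** The 0.8 refers to the first examination only. Total lesions = 0.8/(1 − miss rate). At the average miss rate of 22.5% this is 0.8/0.775 = 1.03 per patient (about 135 lesions per arm). At 30% it is 0.8/0.70 = 1.14 (about 150 per arm).

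**3. Design effect.** DE = 1 + (E[m²]/E[m] − 1) × ICC, where m is lesions per patient. With mean μ, the bracket equals μ for Poisson counts and μ(1 + 1/k) for negative binomial counts with dispersion k.

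- ICC 0.05: from 1 + 1.03×0.05 = 1.05 (Poisson) to 1 + 1.14×3×0.05 = 1.17 (k=0.5).
- ICC 0.3: from 1 + 1.03×0.3 = 1.31 to 1 + 1.14×3×0.3 = 2.03.

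An unadjusted test at nominal 5% then has type I error 2 × (1 − Φ(1.96/√DE)): 6.2% at DE 1.1, 7.4% at 1.2, 8.6% at 1.3, 11.0% at 1.5 and 16.6% at 2.

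**4. Simulated type I error.** Beta-binomial misses, 131 patients per arm, 10,000 runs per cell (standard error at 5%: √(0.05×0.95/10,000) = 0.2 points). ICC and count distribution are assumptions. Each cell gives the uncorrected lesion-level chi-square, in %, for null 22.5% / null 30%.

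| Lesion counts | ICC 0 | 0.05 | 0.1 | 0.2 | 0.3 |
|---|---|---|---|---|---|
| Poisson | 4.7 / 4.8 | 5.6 / 5.9 | 6.3 / 6.2 | 7.1 / 8.0 | 9.0 / 9.6 |
| k=1 | 4.9 / 5.3 | 6.1 / 6.8 | 7.3 / 7.8 | 9.7 / 10.0 | 12.2 / 13.0 |
| k=0.5 | 5.0 / 4.9 | 6.4 / 7.3 | 8.6 / 8.8 | 11.4 / 12.7 | 15.5 / 15.9 |

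The extreme ICC 0.3 cells (9.0% at DE 1.31, 15.9% at DE 2.03) agree with the formula in step 3. With continuity correction the range is 3.2–4.0% at ICC 0, 4.7–7.0% at 0.1 and 6.7–13.2% at 0.3. A patient-clustered test stayed at 5.0–6.1% in every cell.

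**5. Simulated power of the clustered test, 30% v 15%.** 6,000 runs per cell; % for 1.03 / 1.14 lesions per patient.

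| Lesion counts | ICC 0 | 0.05 | 0.1 | 0.2 | 0.3 |
|---|---|---|---|---|---|
| Poisson | 85.3 / 88.0 | 82.3 / 85.8 | 80.3 / 85.3 | 77.7 / 81.6 | 74.6 / 78.5 |
| k=1 | 84.6 / 87.9 | 81.4 / 84.9 | 77.7 / 81.1 | 72.7 / 74.7 | 66.7 / 69.5 |
| k=0.5 | 84.7 / 87.2 | 78.7 / 82.8 | 75.5 / 78.6 | 67.0 / 70.3 | 60.5 / 62.8 |

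Under these counts 32–36% (Poisson), 47–49% (k=1) or 55–57% (k=0.5) of patients have no right colon lesion and add nothing to the miss rate.

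**The case against.** The strongest reply is that the inflation belongs to an analysis the plan never states. If the chi-square is confined to patient characteristics, the fault is an unspecified test and the inflation is hypothetical. If the sentence reaches outcomes, as its mention of polyp size suggests, then a test has been named. Neither reading helps the plan: the first leaves the primary test open, and the second gives the unadjusted lesion-level test.

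Other points carry more weight.

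- **Size.** Nothing in the documents supports a particular ICC or over-dispersion. With Poisson counts and an ICC of 0.05 to 0.1, the error is 5.6–6.3%, hardly different from the clustered test. The figures of 12% and above need k=1 with ICC 0.3, or k=0.5 with ICC 0.2 to 0.3.
- **Sample size.** The formula behind 131 is inferred, because the plan names none, and a shortfall in power is not shown: the simulated values lie on both sides of 80%.
- **Examiner.** With two colonoscopists, examiner effects extend across patients, and a patient cluster does not capture them. Stratification by colonoscopist balances them between arms, so they should largely cancel in the comparison.
- **Choice of method.** GEE against Rao-Scott is a matter of preference. The simulations support clustering on patient in general, not one procedure over the other.

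These points limit the size of the problem. They do not supply a primary test or an allowance for clustering.

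**Conclusion.** The concern holds and should be fixed before the primary analysis. Confidence is high that the plan names no test, no interval and no clustering allowance for its primary outcome, and that 131 per arm matches a calculation with one independent lesion per patient. Confidence is moderate about the numerical consequence. There is no inflation at ICC 0. Across ICC 0.1 to 0.3, the uncorrected lesion-level chi-square rejects in 6.2–9.6% of null trials with Poisson counts, 7.3–13.0% with k=1 and 8.6–15.9% with k=0.5. Power of a correct analysis may be above or below the stated 80%. With Poisson counts it holds at 80% or more up to ICC 0.1; with strong over-dispersion it can fall just below 80% at ICC 0.05. Even if the ICC were near zero, a confirmatory trial should not leave its primary test unstated.

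**What to change.** **Statistical analysis section**

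- Name one primary test: a lesion-level comparison of miss rates between arms with the patient as cluster. Suitable choices are logistic GEE with robust standard errors (PROC GENMOD, REPEATED SUBJECT=patient) or a Rao-Scott chi-square (PROC SURVEYFREQ, CLUSTER patient). If GEE is chosen, state whether the stratification factors, colonoscopist and indication, enter the model.
- Report the difference in miss rates with a 95% confidence interval that uses the same clustering.
- Apply the same method to right colon AMR and HPMR, and allow for clustering if polyp size is compared lesion by lesion.
- Beside the ITT statement, say that patients without a right colon lesion contribute no lesions to this analysis, and report their number per arm.

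**Sample size estimation section**

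- State the assumption behind 131 per arm, which on this reading is one independent lesion per patient. Restate the power from the expected lesions per patient and a stated range of ICC. The aim is to show what the planned enrolment can deliver; it does not require enrolling more patients.

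**Cost:** a few lines of protocol wording and SAS code. Lesion histology, location and examination sequence are already to be recorded, so no new data are needed. Intervals will be somewhat wider, and the restated power may come out below 80%.

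### The interim analysis after 131 patients has no stated outcome, decision rule or significance level, so the plan does not secure its two-sided 5% level for the primary test

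*Combined protocol and SAP*

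**What the plan says.** All places are in the combined protocol and SAP.

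- **Statistical analysis**, on the interim: "Interim analysis will be performed after enrollment of 131 patients". This is the only sentence about it. Nothing gives its outcome, purpose, boundary or consequences, or says who sees the result.
- **Statistical analysis**, on significance: "The criterion for statistical significance will be P value <0.05". No analysis is exempted. The only other threshold ("value <0.1 on univariate analysis will be further entered into forward stepwise logistic regression analysis") governs entry of factors into the regression and is not a criterion for significance.
- **Statistical analysis**, on tests: "Chi-square test for categorical variables will be used to assess differences in demographic and clinical characteristics of patients in each group". No test is named for the miss rate itself.
- **Study Outcomes**: "The primary outcome is the right colon combined AMR and HPMR".
- **Sample size estimation**: "With a statistical power of 80% and a two-side significance level of 0.05, 131 patients will be needed in each study arm", and after the 10% allowance, "Therefore, a total of 292 patients (146 patients in each group) will be enrolled". The interim is not mentioned there.
- **Definition**: the miss rate has a lesion denominator, the missed lesions being "divided by the total number of adenoma and hyperplastic polyps detected during both the first and tandem right colon examinations".

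**The concern.** A scheduled analysis, together with one general P<0.05 rule, leaves open two significance tests of the primary outcome, each at the full level. The level of the primary comparison then depends on an unwritten use of the interim. If nothing can be claimed from that look and it does not alter the trial, the level is the stated 5%. If the arms are compared on the primary outcome and a significant result at either look counts as success, the level is higher. Completing enrolment does not remove the excess, because it comes from the second chance to claim and not from stopping. A reader of the final report could not tell which case applied.

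**Working it through.** **Inputs.** From Sample size estimation: two-sided 0.05, 80% power, 30% miss rate with CO2, reduction of 15 percentage points (so 15% with WE), 131 per arm, 10% allowance, 292 in total. From Statistical analysis: interim after 131 enrolled, and P<0.05 throughout.

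**1. The plan's own figure.** Two proportions, unpooled variance:

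n = (1.960 + 0.842)² × (0.30×0.70 + 0.15×0.85) / 0.15² = 7.849 × 0.3375 / 0.0225 = 117.7

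With continuity correction:

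n = (117.7/4) × [1 + √(1 + 4/(117.7×0.15))]² = 130.7, so 131 per arm

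Then 131/0.9 = 145.6, so 146 per arm and 292 in total. The figure reproduces with the whole 0.05 spent on one test and no allowance for a second look.

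**2. Level if both looks can support a claim at P<0.05.** Under the null, let Z1 (interim) and Z2 (final) be bivariate normal with correlation √t, where t is the information fraction.

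Type I error = 1 − P(|Z1| < 1.960 and |Z2| < 1.960)

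| Reading of the interim | t | √t | Type I error |
|---|---|---|---|
| 131 of 292 enrolled | 0.449 | 0.670 | 8.5% |
| 131 of 262 evaluable target | 0.500 | 0.707 | 8.3% |
| 131 per arm, 262 of 292 | 0.897 | 0.947 | 6.5% |
| Lesion fraction 0.40 (assumption) | 0.400 | 0.632 | 8.6% |
| Lesion fraction 0.55 (assumption) | 0.550 | 0.742 | 8.1% |

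The third row is included because the interim count equals the per-arm target. The literal reading is 131 in total. The second row divides enrolled patients by an evaluable target. Applying the plan's 10% allowance gives 131×0.9 = 118 evaluable, and 118/262 = 0.45, so 8.5% is the more consistent figure for 131 in total.

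**3. Level if the interim supports no claim.** With one test at the end, at a sample size not altered by between-arm results, the level is 5.0%.

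**4. A two-look rule that holds 5%.** Take P<0.001 at the interim and P<0.049 at the end. Whatever t is, the error cannot exceed 0.001 + 0.049 = 0.050. The computed error is 4.93% at t = 0.449, 4.92% at t = 0.500 and 4.94% at t = 0.40. Power, at the drift that gives 80.0% for a single look (1.960 + 0.842 = 2.802), is 79.8% at t = 0.449 and at t = 0.500. A final threshold of 0.0497 would recover slightly more power (about 79.96% at t = 0.449), but its error is 5.006% at t = 0.40, so it does not hold at every fraction.

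**The case against.** The strongest reply is that the plan nowhere provides for an interim efficacy claim or for early stopping, and fixes enrolment at 292. On that reading the trial runs to its target, is tested once, and keeps 5%. The 8.5% needs three things the documents do not state: that the interim compares the arms, that it does so on the primary outcome, and that success may be claimed at either look. This is correct. A reader might infer that the trial as planned has an 8.5% false-positive rate; the documents do not support that.

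What remains is that nothing excludes that use either. The look is a firm commitment, and the one significance rule in the plan covers it without exception.

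Three further points stand:

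- Barring an interim claim does not by itself secure 5%. If between-arm results were used to change the final sample size and the last test stayed at P<0.05, the level could still move. The fixed 292 mitigates this, but the plan does not say that it holds regardless of the interim.
- A boundary is prespecified only if written before the arms are compared. The Methods section reports more than 90 patients completed by the end of May 2019, after an April start, and an amendment approved on 19 July 2019. If that pace held (assumption: 90 in two months, 45 a month), the remaining 41 would take 41/45 = 0.9 months, so 131 would have been reached around the end of June 2019. The documents do not say whether the interim had taken place, and a reader should not infer that it had.
- The choice among valid boundaries is a matter of preference.

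**Conclusion.** The concern holds as a conditional one. The plan schedules an interim analysis under a blanket P<0.05 and spends the full two-sided 0.05 elsewhere on a single test, so the level of the primary comparison is not defined. It is 5.0% if the interim supports no claim and changes nothing. It is about 8.5% (8.3% with 262 as denominator) if the primary outcome is tested at P<0.05 at both looks with success at either, and 6.5% if the interim was meant at 131 per arm.

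These values are nominal. They treat patients as a proxy for lesion information and assume that each single test has exact 5% size. Lesions cluster within patients and no test is named for the miss rate, so neither assumption is guaranteed. The point should be settled before the primary result is interpreted, since it concerns the error rate of the trial's main claim.

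**What to change.** In the Statistical analysis section, confirm that 131 is the total enrolled, and state one of two rules.

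- **(a) No efficacy use of the interim.** There is no between-arm efficacy test at the interim, or a non-binding futility look only. No efficacy claim follows from it. The enrolment target of 292 is not changed on the basis of between-arm interim results. The primary outcome is tested once, at the final analysis, at two-sided P<0.05.
- **(b) A two-look test, available only if no between-arm data have yet been seen.** The right colon combined AMR and HPMR is tested at P<0.001 at the interim and P<0.049 at the final analysis, in place of the general P<0.05 for this outcome.

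If a between-arm look has already happened, disclose it, and report its result and how it was used.

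**Cost.** One or two sentences and no extra patients. Rule (a) without a between-arm test loses no power. With a futility look, if the trial stopped whenever WE was not ahead of CO2 at the interim (an example rule, assumed here), power would be 79.4% at 131/292 or 79.7% at 131/262. Rule (b) makes the final threshold slightly stricter and costs about 0.2 percentage points of power (80.0% to 79.8%).

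### Randomisation is stratified by colonoscopist and indication, but the plan brings neither factor into any comparison of water exchange with CO2; adding them is a nearly free, optional improvement

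*Combined protocol and SAP*

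**What the plan says.** The Randomization section allocates 1:1 and says that stratification based on "colonoscopists and colonoscopy indications (screening, surveillance, and positive FIT) will be performed". Under Colonoscopy Procedures, "Colonoscopies will be performed by two board-certified colonoscopists". With three indications, that makes up to six strata.

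Under Study Outcomes, "The primary outcome is the right colon combined AMR and HPMR", followed by ADR and related detection measures as secondary outcomes.

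The Statistical analysis section mentions neither stratification factor. Its t, Wilcoxon and chi-square tests "will be used to assess differences in demographic and clinical characteristics of patients in each group". No test is named for the miss rate or for any detection rate. One regression is described: "Factors associated with adenoma detection by the first examiner will be identified by univariate analysis", after which factors with a P "value <0.1 on univariate analysis will be further entered into forward stepwise logistic regression analysis". Its declared purpose is to describe the "influence of various factors on adenoma detection". No candidate list, entry level or forced term is stated, so a reader cannot tell whether arm, colonoscopist or indication will be in the model.

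**The concern.** Analysis should normally follow the randomisation. Stratifying balances the arms on colonoscopist and indication, which lowers the true variance of the difference between arms. A test that ignores the strata still uses the larger, unstratified variance. If the strata are prognostic, that test rejects less often than its nominal level and gives away power that the design has already secured.

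What is at stake is some precision on the miss rate and the detection rates. There is also a lesser risk: the only adjusted odds ratios promised come from a data-driven model that was not written to estimate the effect of WE.

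**Working it through.** **The plan's own figure.** The documents give no number on this point. The Sample size estimation section sets the scale: 131 / 0.9 = 145.6, rounded up to 146 per arm, and 2 × 146 = 292. It assumes a 30% miss rate under CO2, a reduction of 15% (read as absolute, to 15%), and 0.8 lesions per patient found at the first right colon examination.

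**Assumptions not in the documents.** Colonoscopists share patients 50/50; indications are 50/30/20%; blocks of 4; the stratum effects are those shown in the tables. The comparator without strata is also assumed, because the plan names no test for these outcomes.

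**1. ADR: size of an unadjusted chi-square test, by hand.** With balance inside each stratum, the variance of the difference is driven by W = Σ w p(1−p). The unadjusted test uses T = m(1−m), where m = Σ w p. Its real type I error is therefore about 2Φ(−1.96/√(W/T)).

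Take the strongest case: ADR 25/50/70% by indication and a colonoscopist OR of 2.5, split evenly on the logit scale.
- Stratum rates are 0.345, 0.613, 0.787 for one colonoscopist and 0.174, 0.387, 0.596 for the other, with weights 0.25, 0.15, 0.10 each.
- m = 0.418, so T = 0.418 × 0.582 = 0.2433; W = 0.2045; W/T = 0.841.
- 1.96/√0.841 = 2.138, which gives a two-sided error of 3.3%.

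The other two cases follow in the same way. The simulated columns compare a Pearson chi-square with a likelihood-ratio test that includes the strata (40,000 null and 40,000 effect trials per case, n = 292, arm OR 1.5 for power).

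| ADR by indication; colonoscopist OR | W/T | Type I by hand | Type I simulated, without vs with strata | Nominal power, without vs with | Size-matched gain |
|---|---|---|---|---|---|
| 40/50/60%; 1.3 | 0.972 | 4.7% | 4.9 vs 5.0% | 40.1 vs 40.6% | 0.1 points |
| 30/50/65%; 1.8 | 0.905 | 3.9% | 4.1 vs 5.3% | 34.2 vs 37.5% | 0.7 points |
| 25/50/70%; 2.5 | 0.841 | 3.3% | 3.4 vs 5.3% | 29.6 vs 35.7% | 0.5 points |

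Size-matched means that each test uses its own empirical 5% critical value. The nominal power differences are 0.5, 3.3 and 6.1 points. The small size-matched gains show that most of this is the removal of conservatism.

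A separate simulation with stratified Cochran-Mantel-Haenszel (CMH) tests, 6,000 trials per cell, gave type I error of 5.3/4.2/3.2% unadjusted against 5.5/5.3/4.9% stratified. Power was 39.6/34.5/28.2% against 39.8/37.4/34.3%.

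**2. Primary miss rate.** This was a lesion-level logistic model with patient-clustered standard errors: n = 292, about 308 lesions, and miss rates of 30% and 15% for an average patient. Further assumptions were gamma-Poisson lesion counts (shape 1) and a patient SD of 0.7 on the logit scale. Each scenario had 60,000 null and 60,000 effect trials.

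| Colonoscopist OR on missing; indication trend OR | Size-matched power, without vs with strata | Gain (simulation SE) |
|---|---|---|
| 1.3; 1.0 | 78.7 vs 78.5% | −0.2 (0.1) |
| 2; 1.2 | 76.7 vs 77.7% | +1.0 (0.2) |
| 3; 1.3 | 73.0 vs 76.1% | +3.2 (0.3), from unrounded values |

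With 262 patients the gains are −0.4, +0.5 and +3.3 points. Type I error with the uncorrected clustered standard error is 5.0–5.4% without strata and 5.6–5.8% with them. The Kauermann-Carroll correction brings these to 4.8–5.2% and 5.0–5.2%.

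**3. Sparse outcomes.** With assumed event rates by indication of 2/4/8% and 1/2/5%, as right colon advanced ADR might show, null rejection was 4.7% and 4.4% for chi-square. It was 6.2% and 7.8% for the adjusted likelihood-ratio test, and 4.7% and 4.9% for CMH.

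**The case against.** **The effect is small and rests on assumed inputs.** This stands. The size-matched gain on the primary outcome is nil when the strata are weak. The +3.2 points need a colonoscopist OR of 3, which is an assumed high value. It should not be read as an upper bound either: "All colonoscopists have performed more than 1000 conventional colonoscopies" sets a minimum of experience and does not limit how far two endoscopists differ.

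**It depends on a larger gap.** This also stands. No between-arm method is given for the miss rate, so stratum adjustment refines an analysis that must first be written. It is still a separate line of that analysis, and it applies to the detection rates as well.

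**The named tests may be meant more widely.** Polyp size, the example given for the Wilcoxon test, is a lesion finding, so the tests might extend beyond patient characteristics. Even so, none of them brings in the strata.

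**A reader might infer that the WE effect will be taken from the stepwise model and so be exaggerated.** The documents do not support that. It would need arm to be a candidate and its retained odds ratio to be quoted as the effect of WE against CO2, and neither is stated. If both held, with a true OR of 1.5, the mean retained OR would be 1.84–1.96 (entry at P<0.10) or 1.91–2.01 (entry at P<0.05), against 1.56–1.57 in a fixed model. At P<0.05, arm is retained in only about 41/39/33% of trials across the three cases. This is ordinary selection on significance and is not a result of the stratification.

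**Adjustment has pitfalls of its own.** An adjusted odds ratio is conditional on the strata, whereas the sample size is planned on miss percentages. The miss rate also involves two endoscopists, so the word colonoscopist is ambiguous. Both points are sound and shape the fix.

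**Conclusion.** The omission is real and minor. The trial randomises within strata that its analysis plan never uses in a between-arm comparison. A reader might take this to invalidate the tests or to inflate false positives; the calculations show neither.

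The consequence is conservatism of an unadjusted ADR chi-square (about 3–4% instead of 5% under moderate to strong assumed effects) and a modest loss of power. That loss is about 0 to 6 points nominal for ADR and about 0 to 3 points size-matched for the primary outcome. The sizes rest on assumed stratum effects, an assumed case mix and an assumed unadjusted comparator; the direction does not depend on the particular values, provided that the strata are prognostic. This is a free improvement, rated COULD.

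**What to change.** Pre-specify that every comparison of WE with CO2 includes arm, colonoscopist and indication:
- **Primary miss rate:** include them within whatever lesion-level, patient-clustered analysis the plan adopts, preferably with a small-sample correction to the clustered standard error.
- **ADR and the other detection rates:** use stratified CMH, which is preferable for sparse outcomes such as right colon advanced ADR, or logistic regression.

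Define colonoscopist as the first examiner, and confirm that this is the one used for stratification. Report an adjusted or stratified risk difference beside any odds ratio. Call the stepwise model an exploratory predictor analysis, and do not take the effect of WE against CO2 from it.

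The cost is wording only, since both factors are already recorded for randomisation. The downsides are three extra parameters (one for colonoscopist, two for indication), no gain if the strata are barely prognostic, and a slightly liberal clustered test (5.6–5.8%) if the correction is left out.
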